8.3.2. Method of Detecting AEs and SAEs

The method of recording, evaluating, and assessing causality of AE and SAE and the procedures for completing and transmitting SAE reports are provided in [Appendix 3](#) (Section 10.3).

Care will be taken not to introduce bias when detecting AEs and/or SAEs. Open-ended and non-leading verbal questioning of the participant is the preferred method to inquire about AE occurrences.

8.3.3. Follow-up of AEs and SAEs

After the initial AE/SAE report, the investigator is required to proactively follow each participant at subsequent visits/contacts. For each event, the investigator must pursue and obtain adequate information until resolution, stabilization, the event is otherwise explained, or the participant is lost to follow-up (as defined in Section 7.3).

In general, follow-up information will include a description of the event in sufficient detail to allow for a complete medical assessment of the case and independent determination of possible causality. Any information relevant to the event, such as concomitant medications and illnesses, must be provided. In the case of a participant death, a summary of available autopsy findings must be submitted as soon as possible to Pfizer Safety.

Further information on follow-up procedures is given in [Appendix 3](#) (Section 10.3).

8.3.4. Regulatory Reporting Requirements for SAEs

Prompt notification by the investigator to the sponsor of an SAE is essential so that legal obligations and ethical responsibilities towards the safety of participants and the safety of a study intervention under clinical investigation are met.

The sponsor has a legal responsibility to notify both the local regulatory authority and other regulatory agencies about the safety of a study intervention under clinical investigation. The sponsor will comply with country-specific regulatory requirements relating to safety reporting to the regulatory authority, IRBs/ Independent Ethics Committees (IECs), and investigators.

Investigator safety reports must be prepared for SUSARs according to local regulatory requirements and sponsor policy and forwarded to investigators as necessary.

An investigator who receives SUSARs or other specific safety information (eg, summary or listing of SAEs) from the sponsor will review and then file it along with the SRSD(s) for the study and will notify the IRB/IEC, if appropriate according to local requirements.

8.3.5. Exposure During Pregnancy or Breastfeeding, and Occupational Exposure

Pregnancies of a partner should be recorded using the Pregnancy Initial Report Form. Pregnancies should be followed until final outcome is known. All follow-up for a pregnancy should be submitted on a Pregnancy Follow-up Report Form.

8.3.5.1. Exposure During Pregnancy (EDP)

- Details of all pregnancies in female partners of male participants will be collected after the start of study intervention and until end of study participation.
- If a pregnancy is reported, the investigator should inform the sponsor within 24 hours of learning of the pregnancy and should follow the procedures outlined in [Appendix 4](#) (Section [10.4](#)).
- Abnormal pregnancy outcomes (eg, spontaneous abortion, fetal death, stillbirth, congenital anomalies, ectopic pregnancy) are considered SAEs.

8.3.5.2. Exposure During Breastfeeding

Not Applicable for this study.

8.3.5.3. Occupational Exposure

An occupational exposure occurs when a person receives unplanned direct contact with the study intervention, which may or may not lead to the occurrence of an AE. Such persons may include healthcare providers, family members, and other roles that are involved in the trial participant's care.

The investigator must report occupational exposure to Pfizer Safety within 24 hours of the investigator's awareness, regardless of whether there is an associated SAE. The information must be reported using the CT SAE Report Form. Since the information does not pertain to a participant enrolled in the study, the information is not recorded on a CRF; however, a copy of the completed CT SAE Report Form is maintained in the investigator site file.

8.3.6. Cardiovascular and Death Events

Not applicable for this study.

8.3.7. Disease-Related Events and/or Disease-Related Outcomes Not Qualifying as AEs or SAEs

Bleeding episodes as part of the natural history of severe hemophilia are not reported as AEs.

8.3.7.1. Lack of Efficacy

Lack of efficacy is reportable to Pfizer Safety only if associated with an SAE.

8.3.8. Medication Errors

Medication errors may result from the administration or consumption of the study intervention by the wrong participant, or at the wrong time, or at the wrong dosage strength.

Exposures to the study intervention under study may occur in clinical trial settings, such as medication errors.

Safety Event	Recorded on the CRF	Reported on the CT SAE Report Form to Pfizer Safety Within 24 Hours of Awareness
Medication errors	All (regardless of whether associated with an AE)	Only if associated with an SAE

Medication errors include:

- Medication errors involving participant exposure to the investigational product;
- Potential medication errors or uses outside of what is foreseen in the protocol that do or do not involve the participating participant.

Such medication errors occurring to a study participant are to be captured on the medication error page of the CRF, which is a specific version of the AE page.

In the event of a medication dosing error, the sponsor should be notified immediately.

Whether or not the medication error is accompanied by an AE, as determined by the investigator, the medication error is recorded on the medication error page of the CRF and, if applicable, any associated AE(s), serious and non-serious, are recorded on an AE page of the CRF.

Medication errors should be reported to Pfizer Safety within 24 hours on a CT SAE Report Form only when associated with an SAE.

8.4. Treatment of Overdose

For this study, any dose of SB-525 (PF-07055480) greater than the intended dose for the participant will be considered an overdose.

Sponsor does not recommend specific treatment for an overdose.

In the event of an overdose, the investigator/treating physician should:

1. Contact the medical monitor immediately.
2. Closely monitor the participant for any AEs/SAEs and laboratory abnormalities.
3. Document the quantity of the excess dose as well as the duration of the overdose in the CRF.

4. Overdose is reportable to Safety **only when associated with an SAE**.

8.5. Pharmacokinetics

8.5.1. AAV2/6 Vector Shedding

AAV2/6 genome in plasma, saliva, urine, stool, and semen by polymerase chain reaction (PCR) will be assessed as described in the SoA ([Table 1](#)). On Day 0, vector genome titer should be obtained in plasma only at 12 hours from the start of the infusion \pm 1 hour.

After Week 12, collection will only continue until three consecutive negative samples are obtained on a sample-type basis (Weeks 16, 20, 24, 28, 32, 36, 40, 44, 48, and 52 [\pm 1 week] and every 1 month after Week 52 to Month 60 [\pm 1 month]). For example, after urine sample results are negative 3 consecutive times, the urine sample will stop being collected while the other samples may continue to be collected if they continue to be positive.

8.6. Pharmacodynamics

Blood samples will be drawn to further explore the study drug mechanism of action and immune responses. These may include, but are not limited to, sEGFR, Gal3BP, von Willebrand factor (vWF), FVIII antigen levels, IL6 and CRP as specified in the SoA ([Table 1](#)).

At each visit where vWF is planned, one plasma sample will also be banked to allow for any additional exploratory assessments.

In addition, weekly assessments of FVIII antigen may be required if a participant is receiving steroids or develops an inhibitor or if warranted by changes in FVIII activity.

Blood samples will be collected and processed according to the instructions provided in the laboratory manual.

8.7. Genetics

FVIII gene sequencing will be performed at screening but only for participants with no prior FVIII sequencing.

A blood sample for DNA isolation will be collected. In the event of DNA extraction failure, a replacement genetic blood sample may be requested from the participant.

See [Appendix 5](#) for information regarding genetic research. Details on processes for collection and shipment and destruction of these samples can be found in the Laboratory Manual.

8.7.1. Specified Genetics

Genetics (specified analyses) are not evaluated in this study.

8.8. Biomarkers

Biomarkers are not evaluated in this study.

8.9. Health Economics

Health economics/medical resource utilization and health economics parameters are not evaluated in this study.

9. STATISTICAL CONSIDERATIONS

Detailed methodology for summary and statistical analyses of the data collected in this study is outlined here and further detailed in a statistical analysis plan (SAP), which will be maintained by the sponsor. The SAP may modify what is outlined in the protocol where appropriate; however, any major modifications of the primary endpoint definitions or their analyses will also be reflected in a protocol amendment.

9.1. Estimands and Statistical Hypotheses

There are no statistical hypotheses and estimands needed for this study.

9.2. Sample Size Determination

This study will enroll approximately 20 participants. Participants who do not complete at least 12 months of the study may be replaced, except participants who experience toxicity due to AEs considered related to study drug and discontinue the study for that reason. These latter participants will not be replaced. In addition, participants who experience transaminitis resulting in loss of efficacy prior to week 4 will not be used to determine dose cohort assignment for subsequent participants. As this is an adaptive design study, the number of participants to be treated at any given dose level will be determined by the available efficacy and safety data in proceeding participants and will not be based on statistical calculations.

9.3. Analysis Set

For purposes of analysis, the following populations are defined:

Population	Description
Enrolled	All participants who sign the ICF and meet all inclusion/exclusion criteria.
Safety	All participants enrolled in this study who receive any portion of study drug and have at least one post-baseline safety assessment will be included in the safety population. All participants who enrolled in the study and received the study intervention.
Evaluatable	All participants enrolled in the study and take the full dose of study intervention and no significant interruption of efficacy measurement.

9.4. Statistical Analyses

All analyses of safety will be performed on the safety population, and participants will be analyzed according to the actual treatment they received. Efficacy analyses will be performed using descriptive methods. No formal statistical analysis of study data is planned.

The SAP will be developed and finalized before database lock and will describe the participant populations to be included in the analyses, and procedures for accounting for missing, unused, and spurious data. This section is a summary of the planned statistical analyses of the primary and secondary endpoints.

9.4.1. Primary Endpoints Analyses

Safety analyses will be performed on data from all participants in the Safety Population.

The incidence of AEs and SAE will be tabulated by dose and overall across dose groups. The rate of occurrence for each adverse event will be summarized by body system, severity, and relation to the administration of PF-07055480. All serious adverse events will be summarized separately.

Additional descriptive analyses to support the primary endpoint will include changes from baseline in clinical laboratory variables (including FIX inhibitor and laboratory parameters for thrombotic potential), vital signs, and vector shedding analysis.

The time course profile of FVIII activity will be determined by measuring changes in circulating FVIII activity.

9.4.2. Secondary Endpoints Analyses

The clinical impact on hemophilia after dosing with SB-525 (PF-07055480) will be determined from the summarization of the change from baseline in the use of FVIII

replacement therapy and the frequency and severity of bleeding episodes. Changes from baseline in the EQ-5D-5L will also be summarized.

The immune response to SB-525 (PF-07055480) will be evaluated from the summarization of FVIII inhibitor levels. Summarization of vector shedding data will include vector DNA detection by PCR in plasma, saliva, urine, stool, and semen.

9.4.3. Exploratory Endpoints Analyses

The impact of potentially relevant circulating factors on FVIII activity will be assessed by summarization of vWF, CRP, IL6, and FVIII antigen. Immune response will be studied by measuring neutralizing activity and antibodies to AAV2/6, as well as Interferon-gamma ELISPOT.

Change from the preceding year values may be calculated for selected clinical and laboratory parameters. Shift-tables (change-from-baseline relative to the normal range) may be constructed for selected laboratory parameters. Participants will continue to be followed for years 2 through 5 to gain additional data on safety and durability of effect.

Details for additional exploratory endpoint analyses (eg. optional liver biopsy) will be provided in the SAP.

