6.5. Concomitant Therapy

All concomitant medications and therapy taken through Month 36 must be captured in the CRF. After Month 36, only concomitant medications and therapy associated with SAEs, AEs related to the study drug, or to AEs with an unknown cause will be reported through Month 60 or the ETV, if applicable. See Section [8.3.1](#) for AE reporting requirements.

The investigator will record all concomitant medications including those given in treatment of AEs on the concomitant medication page in the participant's CRF. Any medication taken by the participant from 30 days prior to screening throughout the course of the study, including over-the-counter medicinal products, dietary supplements, and herbal medications, should be recorded on this form. A short course of prednisone may be instituted either as prophylaxis or post AAV exposure if an immune reaction to the AAV capsid develops (Section [10.7](#)). Any treatment with prednisone and pre-treatment with acetaminophen and diphenhydramine hydrochloride should be recorded on the concomitant medications page.

Participants enrolled in this study who previously received prophylactic FVIII replacement regimens will be required to switch to on-demand therapy approximately 2 weeks after infusion with SB-525 (PF-07055480), pending data shows it is safe to do so. The use and timing of FVIII replacement will be monitored closely in this study and will influence the timing of PD assessments for FVIII activity. There is no washout period per se, but all participants will be switched to an on-demand regimen approximately 2 weeks after infusion and subsequently modulate their FVIII replacement use according to their needs. All participants are to carefully record the date and time of each FVIII administration in an e-Diary, so that the elapsed time between their last FVIII administration and each FVIII level collection can be collected. For participants using short half-life replacement products, the resulting FVIII levels are valid only if elapsed time is more than 48 hours. For participants using extended half-life FVIII replacement products, this time is extended to 72 hours. Of note, 48 and 72 hours are reference values, these times can be modified depending on the participant profile (slow versus fast metabolizers) and the prescribing information of each product. The investigator may recommend a different time for his/her study participant after discussion with the medical monitor.

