Per protocol, if a participant has FVIII replacement therapy around the day of a visit when FVIII activity measurement is scheduled, sample collection should be postponed at least 48 or 72 hours based on the FVIII product used (standard half-life or extended half-life respectively). For all FVIII activity summaries and analyses (including plots), any FVIII activity values measured within 96 hours after administering exogenous FVIII replacement therapy will be excluded as ineligible. In addition, FVIII activity assessments collected after a participant initiates or resumes a prophylaxis regimen will be excluded. If there are multiple observations for an individual in the same time window, for all FVIII activity analyses with the exception of geometric mean analyses, the average of an individual's FVIII activity values within the same time window will be used.

A listing of individual FVIII activity values for each participant will show assay used, observed values in collected units and in % normal units, visit name (including unscheduled visits), and the analysis visit (the visit to which the value has been slotted, either from the visit name, or derived by taking the integer part of relative day/7). Measurements within 96 hours after a FVIII replacement infusion or after a participant initiates or resumes a prophylaxis regimen, will be flagged in the listing and excluded from plots.

Group-level plots will be limited to protocol-defined study visits. If the derived week for an unscheduled assessment falls within the visit window of a protocol-defined visit, the unscheduled value will be displayed. Individual-level plots will use unslotted unscheduled

visit data points. Baseline for FVIII activity is defined as the latest valid measurement prior to IP infusion.

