### **6.3.1. FVIII Antigen**

FVIII antigen levels will be summarized by visit and dose level and presented in a data listing.

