### **6.3.2. Immunogenicity**

The results of the following parameters will be presented in a data listing. Individual profile plots of the values over time will be presented by dose level, if appropriate.

- Total and neutralizing antibodies to AAV2/6;
- Cellular responses against FVIII and AAV2/6 (ELISPOT assay);
- Measurements of CRP and IL6.

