### **6.3.3. Von Willebrand Factor**

Von Willebrand Factor will be summarized for observed values and change from baseline by visit and dose level and presented in a data listing.

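### Protocol 9.4.3 promises to assess the impact of circulating factors on FVIII activity, but no planned output relates any of them to FVIII activity

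*Protocol*

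**What the plan says.** Protocol 9.4.3 gives the aim and the method in one sentence: "The impact of potentially relevant circulating factors on FVIII activity will be assessed by summarization of vWF, CRP, IL6, and FVIII antigen".

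The SAP carries this out factor by factor:

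- vWF (SAP 6.3.3): "Von Willebrand Factor will be summarized for observed values and change from baseline by visit and dose level and presented in a data listing".
- FVIII antigen (SAP 6.3.1): "FVIII antigen levels will be summarized by visit and dose level and presented in a data listing".
- CRP and IL6 (SAP 6.3.2, where the list includes "Measurements of CRP and IL6"): "The results of the following parameters will be presented in a data listing". Individual profile plots over time follow if appropriate.

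Two further rules decide which FVIII values could be paired with these factors. SAP 3.1.2 provides that "any FVIII activity values measured within 96 hours after administering exogenous FVIII replacement therapy will be excluded as ineligible", and it also drops values obtained once a prophylaxis regimen has been started or resumed. On the timing of the change from prior prophylaxis, Protocol 6.5 says: "There is no washout period per se, but all participants will be switched to an on-demand regimen approximately 2 weeks after infusion".

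**The concern.** An impact of one variable on another can be seen only when the two are looked at together, in the same participant at the same time. The plan describes vWF, CRP, IL6 and FVIII antigen separately and describes FVIII activity separately again. A reader of the study report who wants to know whether FVIII activity moved with vWF will find two sets of by-visit tables that cannot say.

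The FVIII time course is a primary endpoint, and the protocol itself calls these factors potentially relevant to it. At stake is whether the report delivers the exploratory reading of that time course that Section 9.4.3 promises. The primary and secondary results themselves are not at stake.

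**Working it through.** The documents give no sample-size, power or precision figure for this aim, so there is no stated number to reproduce. The check has three parts.

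**1. Does any planned output relate these factors to FVIII activity?**

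- SAP 6.3.1 and 6.3.3: by-visit, by-dose summaries and listings of antigen and vWF. FVIII activity is not involved.
- SAP 6.3.2: listing and possible profile plots of CRP and IL6. FVIII activity is not involved.
- SAP 6.1.2: one scatter plot, of chromogenic against one-stage FVIII results.
- SAP 6.5.4: one overlay for Cohort 4, of liver function, FVIII activity and corticosteroid use.

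So the SAP has joint displays, but none includes vWF, CRP, IL6 or antigen. That separate summaries carry no information about a relation is true by construction, and a small example shows it. Twenty simulated vWF values with mean 108.88, median 112.05 and SD 42.4 were re-paired with one fixed set of FVIII values. The vWF summary stayed identical while the Spearman correlation was +1.00, -0.03 or -1.00.

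**2. Do the data for vWF exist?**

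From the Schedule of Activities, the visits after the switch to on-demand treatment with both vWF and FVIII activity are:

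- Weeks 4, 8 and 12: 3.
- Weeks 16 to 52 in steps of four: (52 - 16)/4 + 1 = 10.
- Months 24, 36, 48 and 60: 4.
- Total: 3 + 10 + 4 = 17 per participant.

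Seventeen is a ceiling. Pairs are lost where FVIII falls within 96 hours of replacement or after prophylaxis starts or resumes.

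**3. What is possible for CRP and IL6?**

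The Schedule of Activities draws them at Baseline and Day 7 only. Baseline is about a week before the vector, which leaves one post-infusion value. It precedes Week 9, the start of steady state named in SAP 6.1.2.1.

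Whether the Day 7 FVIII value is eligible depends on the participant's regimen, because prior prophylaxis may run to about Week 2 (Protocol 6.5, SAP 3.2):

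- Standard products, about three infusions a week (Protocol 2.2.1): mean interval 168/3 = 56 h. A schedule of 48, 48 and 72 h keeps every gap below 96 h, so the value is excluded.
- Longer half-life products, about 1.5-fold (Protocol 2.2.1), assuming the interval scales with half-life: mean 1.5 x 56 = 84 h, but longest gap 1.5 x 72 = 108 h. The value is usually excluded, though not always.
- On-demand participants, eligible with at least 12 bleeds a year (Protocol 5.1), assuming Poisson bleeds and one infusion day each: 1 - exp(-12 x 4/365.25) = 12% excluded.

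The documents do not give the share on prophylaxis. If every prophylaxis value is excluded, the expected exclusion is s + (1 - s) x 0.12 for share s: 12% at s = 0, 56% at s = 0.5 and 100% at s = 1.

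**The case against.** The strongest reply is that this is one loosely worded sentence and not a failed endpoint. Protocol Table 2 and SAP 2.1 define the endpoint as measurements of vWF, CRP and IL6, in support of mechanism of action and immune response, and the SAP delivers those measurements. Everything is declared descriptive, and Protocol Section 9 lets the SAP modify what the protocol outlines. This stands as a limit on severity. It does not remove the mismatch: a paired plot is also descriptive, and Section 9.4.3 still promises an assessment of impact.

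Four stronger readings are tempting, and the documents do not support them.

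- A reader might infer that FVIII values at the CRP/IL6 draws are largely excluded across the trial. That follows only for participants on frequent regular prophylaxis. On-demand participants are eligible and the mix is not stated.
- A reader might infer from SAP 6.3.2 that CRP and IL6 get less than the summarization the protocol promises. But SAP 6.6.2 commits to summarizing the tests specified in SAP 3.5.2, which points to Protocol Appendix 2, where CRP and IL6 appear. The two SAP sections need reconciling; a shortfall is not established.
- A reader might assume five Cohort 4 participants, multiply by 17 to get 85 pairs, and expect a tight interval. For r = 0.5 with 85 - 5 - 1 = 79 degrees of freedom, tanh(0.549 ± 1.96/√79) gives 0.32 to 0.65. The cohort size is assumed, exclusions reduce the count, and serial values are not independent. With first-order autocorrelation of 0.5 in both series (assumed), simulated coverage of that nominal 95% interval falls to about 88%.
- A reader might expect a paired analysis to separate vWF-driven fluctuation from changing transgene expression. It cannot do so by itself: if both drift over time, they correlate within participants even when neither affects the other.

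**Conclusion.** The concern holds in a limited form. The stated method in Protocol 9.4.3 cannot answer the stated question, and the SAP adds nothing that could. This rests on the text alone and needs no numerical assumption.

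For vWF, the material for a better display is already scheduled: up to 17 paired visits per participant, fewer after exclusions. For CRP and IL6, the firm point is that only one scheduled post-infusion value exists, so no later change in FVIII can be set against a concurrent value. Any relation would rest on one point per participant. At n = 5 (assumed), an observed correlation of 0.5 has a 95% interval of tanh(0.549 ± 1.96/√2), that is -0.68 to 0.96; even at n = 20 it is 0.07 to 0.77. A listing is about as much as these data can bear.

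Severity is minor. The endpoints are exploratory, and no primary or secondary conclusion or dose decision changes.

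**What to change.** - **vWF (SAP 6.3.3).** Pair each vWF value with the eligible central-laboratory FVIII activity from the same visit, under the exclusions in SAP 3.1.2. Show per-participant overlays or scatter plots for Cohort 4, separately for the chromogenic and one-stage assays, and report how many pairs remain. If a within-participant log-scale slope or correlation is added, label it descriptive and note that shared time trends and serial correlation limit its interpretation.
- **CRP and IL6.** Either list each Cohort 4 participant's Day 7 change from baseline beside the Year 1 FVIII geometric mean already defined in SAP 3.1.2.1, or remove both from the impact sentence in Protocol 9.4.3 at the next amendment.
- **Consistency.** Reconcile SAP 6.3.2 with SAP 6.6.2 so that it is clear whether CRP and IL6 are summarized or only listed.

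The cost is one or two additional exploratory outputs and some SAP wording, from samples already scheduled. Only the rewording of Section 9.4.3 requires a protocol change, and it can wait for an amendment made for other reasons.
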